### Sample size calculations:

Sample sizes were calculated at 90% power with alpha of 5%

The sample standard deviation of healing time in days was 26, with the 'worst case' recorded standard deviation being 39.4

The weighted average of healing time for compression only was 75.4 (based on N=1787)

The weighted average of healing time for compression + intervention was 47.3 (based on N=758)

This represents a large effect size of treatment and, even with the 'worst case' SD, would require a sample size of 42 - I feel this is optimistic, likely overestimates the effect size of the intervention and would result in an underpowered study

If, like EVRA, a 15% effect size was considered this would make the healing time estimate for compression + intervention 64.1 days, giving a sample size of 255 (using the 'worst case' recorded standard deviation of 39.4)

Allowing for a dropout rate of 10% and protocol violations the target sample size can be 300 set at patients

With the more lenient SD of 26, and the EVRA effect size of 15%, the sample size is 112

Allowing for a dropout rate of 10% and protocol violations the target sample size can be 130 set at patients

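### The sample size section leaves two enrolment targets open, 300 and 130, and read as trial totals neither gives the stated 90% power at its own SD

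*Protocol*

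**What the plan says.** Everything is in the Protocol, section on sample size calculations. The common premise is "Sample sizes were calculated at 90% power with alpha of 5" per cent. The variability is given twice: "The sample standard deviation of healing time in days was 26, with the 'worst case' recorded standard deviation being 39.4". The control mean is stated as "The weighted average of healing time for compression only was 75.4 (based on N=1787"). Applying a 15% reduction, the section says "this would make the healing time estimate for compression + intervention 64.1 days, giving a sample size of 255", using the larger SD.

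Two targets follow. From the 255: "Allowing for a dropout rate of 10% and protocol violations the target sample size can be 300 set at patients". Then the calculation is repeated with the smaller SD: "With the more lenient SD of 26, and the EVRA effect size of 15%, the sample size is 112". From the 112: "Allowing for a dropout rate of 10% and protocol violations the target sample size can be 130 set at patients".

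Both targets are phrased as possibilities. No sentence states which SD the trial adopts, which target applies, or whether the numbers are per group or for the whole trial. The methods section says that patients are randomised to two groups but gives no allocation ratio. The statistics section promises a separate analysis plan and does not return to the sample size.

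**The concern.** The two targets serve the same comparison at the same power and significance level; only the assumed SD differs. They cannot both be the size of the trial, since 130 is 43% of 300 (130/300 = 0.433). The enrolment target belongs in the protocol, and this protocol does address it, but with two incompatible answers. A team that stops at 130 and a team that goes on to 300 could each say that it followed the text.

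The second difficulty concerns what the numbers count. If 255 and 112 came from a per-group formula and were then carried forward as whole-trial figures, each target holds about half the patients that its own assumptions require. Choosing one target would then not by itself restore the stated power.

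At stake is whether the primary objective, the effect of foam sclerotherapy on time to complete healing, can be answered with the stated assurance.

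**Working it through.** **Inputs, all from the sample size section:** control mean 75.4 days; intervention mean 64.1 days; difference d = 75.4 − 64.1 = 11.3 days; SD 26 or 39.4; power 90%; alpha 5%; dropout 10%. **Assumptions not in the text:** two-sided test, 1:1 allocation. The check uses the protocol's own framework, a comparison of two means with a normal approximation.

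**Step 1: reproduce the plan's figures.** The number per arm is n = 2(1.96 + 1.2816)² SD²/d², where 2(1.96 + 1.2816)² = 21.016.

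- SD 39.4, d = 11.3: 21.016 × 1552.36/127.69 = 255.5 (stated 255)
- SD 26, d = 11.3: 21.016 × 676/127.69 = 111.3, rounded up to 112 (stated 112)
- SD 39.4, d = 75.4 − 47.3 = 28.1: 21.016 × 1552.36/789.61 = 41.3, rounded up to 42 (stated 42, the size that the section sets aside)

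All three agree as numbers **per arm**. As totals they do not: the two-sided totals are 512, 224 and 84, and the one-sided totals are 418, 182 and 68.

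**Step 2: power of each target.** Power = Φ(d/(SD√(2/n)) − 1.96), with n the evaluable patients per arm after 10% dropout.

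- 130 as a total: 130 × 0.9/2 = 58.5 per arm
- 300 as a total: 300 × 0.9/2 = 135 per arm
- 130 per arm: 130 × 0.9 = 117 per arm
- 300 per arm: 300 × 0.9 = 270 per arm

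| Reading | n per arm | SD 26 | SD 39.4 |
|---|---|---|---|
| 130 total | 58.5 | Φ(2.351 − 1.96) = 65% | Φ(1.551 − 1.96) = 34% |
| 300 total | 135 | Φ(3.571 − 1.96) = 95% | Φ(2.356 − 1.96) = 65% |
| 130 per arm | 117 | Φ(3.324 − 1.96) = 91% | Φ(2.194 − 1.96) = 59% |
| 300 per arm | 270 | above 99% | Φ(3.332 − 1.96) = 92% |

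**Step 3: sensitivity of the lowest figure** (130 as a total, SD 39.4). A t-test in place of the normal approximation gives 33.7%. With no dropout at all the power is 37%. A one-sided test with 117 evaluable patients gives 46%.

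**Step 4: difference detectable with 80% power,** (1.96 + 0.8416) × SD√(2/n), targets as totals.

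- 130: 13.5 days at SD 26, 20.4 days at SD 39.4
- 300: 8.9 days at SD 26, 13.4 days at SD 39.4

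The planned difference is 11.3 days.

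**Step 5: what 90% power would need as a total.** At SD 39.4, 512 evaluable, so 512/0.9 = about 569 enrolled. At SD 26, 224 evaluable, so 224/0.9 = about 249 enrolled.

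**The case against.** The best defence is that the two targets are scenarios under two SDs, and that 130 is sound if the SD is 26. That stands in part: the protocol calls 26 the sample SD and 39.4 only the worst case, so 39.4 should not be treated as the expected value. A section that presents scenarios must still end by adopting one, and this one does not.

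A second defence is that the targets may be meant per arm. Then 130 has 91% power at SD 26, 300 has 92% at SD 39.4, and each delivers its promise at its own SD. The arithmetic of 255 and 112 favours this reading; the wording, a target number of patients, favours totals. The protocol does not settle it, and two targets remain on either reading.

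Four stronger inferences are tempting and not supported:

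- **That 34% is the price of not choosing a target.** Much of that shortfall comes from reading per-arm results as totals: on the per-arm reading the same cell is 59%.
- **That the section contradicts itself by setting aside the size of 42 as too small and then allowing 130.** It sets 42 aside because the assumed effect looked too large. The 130 already uses the reduced 15% effect, so that reason does not carry over.
- **That the trial may test at 130 and, if the result is negative, carry on to 300, with an inflated type I error.** No such procedure is described. Any interim rules may stand in the analysis plan, which is not at hand.
- **That nothing anywhere says when enrolment ends.** The protocol refers to an attached time chart that is not available. It may give a recruitment period, though nothing suggests that it selects a target.

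**Conclusion.** The point holds. The protocol gives two incompatible targets for one comparison and selects neither, so the trial has no single size or stated power.

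Read as totals, neither target reaches 90% at the SD from which it was derived: each gives about 65% (130 at SD 26, 300 at SD 39.4). At the other SD, 130 falls to about 34% and 300 rises to about 95%. Read per arm, each target reaches its goal at its own SD, but 130 drops to about 59% if the SD is 39.4.

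These figures rest on a two-sided test, equal allocation, 10% dropout and the protocol's own comparison of means. The first two are assumptions, supported by the fact that they reproduce the protocol's 42 and 112 after rounding up and come within one patient of its 255. The absence of a chosen target depends on none of them.

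A reader might infer that 300 is therefore the right choice. The documents do not support that either: 300 as a total has only about 65% power at the SD used to justify it. The choice is the sponsor's.

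**What to change.** In the sample size section:

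1. Name one SD and one enrolment target, and delete the other target.
2. Label the target as the trial total or as a number per arm, and state the allocation ratio and the sidedness of the test.
3. Replace the general claim of 90% power with the power that the chosen target delivers at both SDs, and give the difference it can detect with 80% power. As totals that is 13.5 to 20.4 days for 130 and 8.9 to 13.4 days for 300.
4. State that the size is fixed in advance and is not chosen on outcome data.

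The cost is one paragraph, and the stated power becomes less favourable if the targets are totals. No extra patients are needed if the sponsor keeps a stated total and reports its true power. Delivering 90% would need about 249 enrolled in total at SD 26, or about 569 at SD 39.4. If the targets were meant per arm, the label alone makes the trial 2 × 130 = 260 or 2 × 300 = 600 patients, and the sponsor should confirm that this is feasible.

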## **Quality of life assessment:**

QoL questionnaire SF-12 Arabic version and VCSS

#### **Documentation:**

- A secure cloud based digital platform will be created
- Upon randomization, the following data will be collected for each participant:
  - o Unique participant number
  - o **Initial visit clinical assessment:** date, age, gender, clinical center, ulcer size in 2 dimensions, ulcer size as measured by Lesionmeter software, ulcer depth (subjective), ulcer location, ulcer side (right or left lower limb), ulcer duration, presence of pedal pulses, ABPI, history of DVT(s), history of venous intervention(s), type of venous intervention (surgery, ablation, foam, stent), date(s) of venous intervention(s), history of diabetes, HbA1C, BMI (weight and height), cardiac failure (including ejection fraction and NYHA classification), other co-morbidities
  - o **Dressings and compression:** type of ulcer dressing and type of compression used; both recorded at each visit
  - Duplex ultrasound findings: details of superficial and deep system reflux and obstruction
  - o **Foam sclerotherapy:** drug used, concentration, gas used, number of injections, foam volumes injected, number of foam sclerotherapy sessions, perforator treatment
  - Follow up visits: date, ulcer healed?, ulcer size in 2 dimensions, ulcer size as measured by Lesionmeter software, ulcer depth (subjective), foam side effects/complications
  - o **Final visit:** ulcer healed?, ulcer size in 2 dimensions, ulcer size as measured by Lesionmeter software, ulcer depth (subjective), foam side effects/complications
  - **Telephone follow up:** date of date, date of recurrence if any, compliance with compression hosiery
  - o **Ulcer photography:** at least one ulcer photograph at the first visit, and one ulcer or ulcer site photograph during the last visit

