#### **Objectives:**

- Primary objective:
  - To assess the effect of foam sclerotherapy of the ulcer veins on time to complete VLU healing

- Secondary objectives:
  - o To chart the rate of ulcer healing at 3, 6, 9 and 12 months
  - o To assess the rate of ulcer recurrence
  - To determine the length of time free from ulcers (ulcer-free time) during the first year after randomization
  - o To report health-related quality of life
  - o To describe the side-effects and complications of foam sclerotherapy

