## **Methods:**

- Patients with open venous ulcers (C6) will be assessed by duplex ultrasound scan for
  - o Superficial venous reflux, and identify its source
  - o Evidence of post-thrombotic reflux and/or obstruction, and characterize this
  - o Evidence of refluxing "ulcer veins" and/or pathologic incompetent perforators in the vicinity of the VLU

- Cross sectional or invasive venography +/- intravascular ultrasound at the discretion of the treating physician, based the upon suspicion of proximal venous outflow obstruction
- Patients with open VLU and/or refluxing ulcer veins and/or pathologic incompetent perforators will be eligible for admission to the study
- Individuals meeting inclusion criteria will be offered a participant information sheet
- Written informed consent will be obtained
- Consented patients will be randomized into two groups:
  - o Group A: Foam sclerotherapy for ulcer veins in addition to appropriate therapy
  - o Group B: Appropriate therapy alone without foam sclerotherapy for ulcer veins
- Appropriate therapy:
  - Superficial venous pathology only: will be treated by ablation of the superficial venous reflux by surgery or endovenous techniques, in addition to treatment of incompetent leg tributaries by phlebectomy or foam sclerotherapy.
  - O Superficial venous reflux associated with deep venous obstruction or reflux: treatment of the superficial venous reflux will be individualized and left to the discretion of the vascular surgeon in charge.
  - Deep venous obstruction and / or reflux: patients with iliac vein obstruction may be considered for iliac vein stenting. Otherwise, patients with deep venous pathology will be treated by compression.
- In all participants, the VLU will be debrided as clinically indicated and, if there is evidence of infection, a course of antibiotics will be prescribed according to the local standard of care
- Compression therapy will be provided by trained personnel according to the local standard of
  care. Multilayer elastic compression (two to four layers), short-stretch compression,
  compression stockings, and adjustable compression wraps are all deemed to be acceptable.
   Details of compression types used will be recorded

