- Foam sclerotherapy: ulcer veins are identified using a linear US probe 7-10Mhz; polidocanol 0.5-1% mixed with gas in a ratio of 1:4 is used to fill the network of refluxing ulcer veins. A total volume of 5-10ml of foam is used per session. Patients are reviewed after 1 week. Foam sclerotherapy may be repeated after one week if the ulcer veins remain patent and the ulcer is not healed. Only two sessions are permitted per lower limb. Following foam sclerotherapy, foam compression is applied
- Ulcer dressing and re-application of compression is performed on a weekly basis until the ulcer is healed
- Following ulcer healing, grade II compression stockings or adjustable compression wraps are prescribed
- After complete healing the patient is followed up monthly by telephone to enquire about ulcer recurrence, and compliance with compression hosiery
- At completion of the study, the patient is reviewed in person

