#### Safety

Any adverse events should be recorded and reported to the PI

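### The protocol wants every adverse event recorded, but its listed data prompt only for foam complications at visits and for no harms by telephone, so harms ascertainment can differ by arm

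*Protocol*

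**What the plan says.** Harms appear in three places in the protocol.

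- **Objectives.** The last secondary objective is "To describe the side-effects and complications of foam sclerotherapy". The End points section lists no safety end point.
- **Safety.** The section is one sentence: "Any adverse events should be recorded and reported to the PI". It is not limited by arm, cause or type of contact. It names no form, time window or way of asking.
- **Documentation.** The entries for follow-up visits and for the final visit both end with "ulcer depth (subjective), foam side effects/complications". Neither lists a general adverse-event item. The telephone entry is a date plus "date of recurrence if any, compliance with compression hosiery".

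Methods sets the contacts. Dressing and compression are weekly until the ulcer heals. Then: "After complete healing the patient is followed up monthly by telephone to enquire about ulcer recurrence, and compliance with compression hosiery". Finally: "At completion of the study, the patient is reviewed in person".

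Methods also defines the comparator, "Group B: Appropriate therapy alone without foam sclerotherapy for ulcer veins". For patients with superficial disease only, however, background therapy in either group is ablation "in addition to treatment of incompetent leg tributaries by phlebectomy or foam sclerotherapy". Foam exposure is therefore not confined to Group A.

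**The concern.** The Safety section asks for everything; the data list asks about one treatment. Staff must decide that foam caused an event before the listed field accepts it. Harms that can occur in either group, such as thrombosis in a post-thrombotic patient, infection, or a complication of ablation or stenting, have no listed field. They rely on someone volunteering a report under the Safety rule.

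Two things are at stake. First, prompted reporting of foam events beside unprompted reporting of everything else is uneven, and the unevenness follows the randomized treatment. Second, a patient who heals moves to calls that ask about no harms, and healing time is what the trial expects foam to change. An analysis plan cannot repair either problem, because it cannot recover events that nobody asked about.

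**Working it through.** No figure in the protocol bears directly on this point, so the check is mainly a comparison of sections.

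**1. What is prompted, by contact**

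| Contact | Harms item listed |
|---|---|
| Follow-up visits | Foam complications only |
| Monthly calls after healing | None |
| Final visit | Foam complications only |
| Safety section (all participants) | All adverse events, but no matching field or prompt |

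**2. To whom the foam field applies (Methods)**

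- Group A: every patient treated as assigned, through ulcer-vein foam.
- Group B, superficial disease only: those whose tributaries are treated with foam rather than phlebectomy. The frequency is not given.
- Group B, superficial reflux with deep disease: treatment is at the surgeon's discretion, so foam is possible but unspecified.
- Group B, deep disease only: compression, or possibly iliac stenting. No foam is described, so the field has nothing to ask about.

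The prompt thus applies to all of Group A and to an unknown part of Group B.

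**3. Whether a foam event can be traced to the randomized intervention**

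The foam entry under Documentation covers the drug, concentration, gas, injections, volumes, sessions and perforator treatment. It does not record whether the injected veins were ulcer veins or tributaries. For a Group A patient who received both, the listed data cannot assign a complication to one or the other.

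**4. How long the unprompted period is**

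Inputs: a 12-month study period (End points) and the mean healing times in Sample size calculations. Assumptions: the final visit falls at day 365 and the patient heals at the mean time without recurrence.

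Unprompted days = 365 − healing time.

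- 75.4 days (compression only): 365 − 75.4 = 289.6 days, or 289.6/365 = 79% of the year.
- 64.1 days (the 15% effect): 365 − 64.1 = 300.9 days, or 300.9/365 = 82%.
- 47.3 days (the larger effect, which the protocol calls optimistic): 365 − 47.3 = 317.7 days, or 317.7/365 = 87%.

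The difference from compression only is 300.9 − 289.6 = 11.3 days for the 15% effect and 317.7 − 289.6 = 28.1 days for the larger one. On these figures the period without a prompt is long in both groups, and its difference between groups is small beside its length.

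**5. Direction**

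The foam-specific field favours recording in Group A. Earlier healing would take Group A patients out of prompted contact sooner and so favour under-recording there. Requiring attribution to foam also removes some unrelated events in Group A. The documents give nothing with which to weigh these against each other.

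**The case against.** The case on the other side is substantial, and much of it stands.

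- **The Safety rule already covers both arms.** It does. A reader might infer from the visit fields that harms cannot be compared at all. The documents do not support that, because events in either group must be recorded under this rule. What is missing is a matching prompt, which makes comparison less reliable rather than impossible.
- **The data list is not a complete inventory.** This is also right. The SF-12 and VCSS required under Quality of life assessment do not appear in it either, and no case report form is shown. Absence from the list is not proof that adverse events will go uncollected. But the list does choose a harms question for visits, and that question is foam-specific. Methods separately states what the calls are for, and harms are not included.
- **The safety objective is descriptive and specific to foam.** True, and no between-arm safety comparison is promised. That limits the severity. Even so, describing the complications of foam requires deciding which events foam caused, and here the same question put to the comparator group helps most.
- **Late events are still caught.** Foam is limited to two sessions per limb with review after one week, visits are weekly until healing, and every patient is seen at the end. A reader might infer that events after healing are lost. They need not be: they can be reported unprompted or recalled at the final visit, although the listed field there is again foam-only.
- **Group B will show almost no events.** A reader might infer a spurious excess in Group A of some stated size. That would require every background event in Group A to be blamed on foam, almost no tributary foam in Group B, and nothing captured under the Safety rule. The documents support none of these and supply no event rate.

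**Conclusion.** The point holds as a mismatch between two sections. The Safety section requires all adverse events, while the only prompted harms item under Documentation is tied to foam and to visits, and the calls after healing prompt for none. Followed as written, this allows ascertainment to differ by arm. It also leaves attribution to ulcer-vein foam insecure.

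The consequence is unreliable harms data, not an impossible comparison. The net direction of bias is unknown, and its size cannot be estimated from the documents. The only size available is the unprompted period of about 290 to 301 days at the planning means (up to 318 with the optimistic figure), under the assumptions stated above. The conclusion also assumes that the listed fields and call content become the forms actually used.

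This should be corrected before data collection, because it is cheap and the omission is hard to repair afterwards. It does not threaten the primary objective.

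**What to change.** Reconcile Documentation with Safety:

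1. Replace the foam-only field with one arm-neutral adverse-event item. Word and ask it identically in both groups at every follow-up visit, every monthly call and the final visit.
2. Record relation to foam as a separate entry made after the event is captured, distinguishing ulcer-vein foam from tributary foam. Add the veins treated to the foam entry so that this can be answered.
3. State in the protocol that adverse events are reported by arm, alongside the existing description of foam complications.
4. Extend the stated purpose of the calls in Methods to include adverse events.

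The cost is a change to the forms and slightly longer visits and calls. No treatment, visit or end point changes.

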## o **Proof of data credibility:** ulcer photography

#### **Exclusion from trial:**

Patient non-compliant with protocol Participant withdrawal of consent

